1.0 Clinical Investigation Plan Overview

The commercially available Günther Tulip[®] and Cook Celect[®] inferior vena cava filters have been previously evaluated in clinical studies.¹⁻³ This prospective, multicenter, single-arm clinical study will further evaluate the safety and effectiveness of Cook's permanent and retrievable inferior vena cava (IVC) filters (specifically, the Günther Tulip[®] and the Cook Celect[®] filters) in patients in need of temporary or permanent IVC filter placement for the prevention of pulmonary embolism (PE). This study will enroll 320 patients in the Celect[®] filter stratum and up to 150 patients in the Günther Tulip[®] stratum at up to 40 clinical sites globally; patients will be stratified based upon the type of filter they receive. Consistent with current clinical practice and already-completed studies of Cook's IVC filters, the study will evaluate the performance and safety of filters in patients considered at risk for PE for a variety of clinical reasons (i.e., a broad patient population).

Study assessments will include, but are not limited to: rate of technical placement success, rate of freedom from new symptomatic PE, rate of freedom from new PE, rate of clinical perforation, rate of migration, rate of filter fracture, rate of filter embolization, rate of IVC thrombotic occlusion, rate of new symptomatic deep vein thrombosis (DVT; total incidence and new incidence), rate of procedure-related complications, time to filter retrieval, number of successful retrievals, and rate of technical retrieval success.

Patients will be followed until 1 month after successful filter retrieval or until study completion 2 years after filter placement. Enrollment is expected to be completed within 2 years of initiating the study. The primary study endpoints for the Celect[®] filter stratum will be compared to performance goals for safety (i.e., freedom from major adverse events) and effectiveness (i.e., technical placement success and freedom from new symptomatic PE while a filter is indwelling). Additional study outcomes will be evaluated separately for each stratum (i.e., separately for patients receiving the Günther Tulip[®] and Celect[®] filters) and for the combined patient set. The study flow diagrams are presented in Figure 1.1 (filter placement and follow-up) and Figure 1.2 (filter retrieval and follow-up).

[figure not shown]
^aImaging performed to document the presence of PE in patients with suspected PE is to be collected

^bImaging performed pre-placement to verify anatomical study criteria and post-placement to verify the position of the filter

^cType of filter is at the discretion of the physician

^dX-ray may be substituted with high quality still shot from venacavagram (2-view) to assess device integrity

Figure 1.1. Study flow diagram (filter placement and follow-up schedule)

^aX-ray may be substituted with high quality still shot from venacavagram (2-view) to assess device integrity

Figure 1.2. Study flow diagram (filter retrieval and follow-up schedule)

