Celect[®] study received filters for these types of indications. Mean follow-up duration (with range in parentheses) was 70.4 ± 49.3 (0-160) days for the IDE Günther Tulip[®] study, 124 ± 75.3 (3-494) days in the second Günther Tulip[®] study, and 277 ± 146 (1-602) days in the Celect[®] study (note: the Celect[®] study included an arm specifically intended to assess permanent filters). Mean filter indwell times (for retrieved filters) were 11.0 days in the IDE Günther Tulip[®] study, 58.9 days in the second Günther Tulip[®] study, and 179 days in the retrieval arm of the Celect[®] study.

The significant safety findings (including PE and those AEs associated with the safety endpoint specified in this clinical investigation plan) in each study are summarized as follows. In the Günther Tulip[®] IDE study, events included one filter misplacement and migration requiring immediate retrieval and placement of a new filter, one filter migration to the right atrium (with successful retrieval), one PE, one patient with a caval thrombosis/occlusion, and four deaths (none were device related); in addition, one patient had a vena cava injury following the retrieval procedure (with a normal 3-month post-retrieval follow-up examination). Events in the second Günther Tulip[®] study included five PEs, one DVT, one filter fracture noted at retrieval, one vascular access site complication following filter implant, and 13 deaths (two were related to PE and six were within 30 days of filter placement). In the Celect[®] study, related events included two PEs, one DVT, one migration (without clinical sequelae), and 26 deaths (one associated with a PE and eight within 30 days of filter placement); there was no difference in the type of events observed in the permanent and retrievable study arms. The incidence of each type of event observed in Cook's clinical investigations is on the low end of, or below, the rates reported in Tables 4.1 and 4.2 above (Table 4.3). Moreover, the overall rate of events associated with the primary endpoints of this clinical investigation (i.e., PE, placement success, caval thrombosis/occlusion, perforation with clinical sequelae, DVT, embolization, fracture, and migration) for the Günther Tulip[®] filter was 3.7% and the overall rate of events for the Celect[®] filter was 9.3%.

Table 4.3. Cook's IVC filter adverse event rates

Outcome Measure	Rate observed in Cook's studies
PE	1.1%
Placement success	0.14%
Caval thrombosis/occlusion	0.14%

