7.2 Point of Enrollment

Patients will be considered enrolled in the study once the filter introducer sheath is inserted below the skin.

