7.13 Participation Endpoints of the Study

A patient's participation in the study will end after any of the following:

- Completion of all scheduled clinical and imaging evaluations to 1 month post-retrieval or 2 years post-placement;
- Device not implanted;
- Patient withdrawal or lost to follow-up;
- Closure of the study; or
- Patient death.

Any data collected on the patient up to a participation endpoint (or until all queries involving the patient are resolved) may be used in the study.

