8.0 Statistical Considerations

8.1 Hypotheses to be Tested

The study hypotheses will be tested only for patients receiving Celect[®] filters. No formal hypotheses will be tested for patients receiving the Günther Tulip[®] filter; rather, summary statistics will be presented for patients receiving the Günther Tulip[®] filter.

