Pulmonary embolism (PE), massive – Acute PE with sustained hypotension (systolic blood pressure < 90 mmHg for at least 15 minutes or requiring inotropic support, not due to a cause other than PE, such as arrhythmia, hypovolemia, sepsis, or left ventricular [LV] dysfunction), pulselessness, or persistent profound bradycardia (heart rate < 40 bpm with signs or symptoms of shock).

² Jaff MR, McMurtry MS, Archer SL, Cushman M, Goldenberg N, Goldhaber SZ, et al. Management of massive and submassive pulmonary embolism, iliofemoral deep vein thrombosis, and chronic thromboembolic pulmonary hypertension: A scientific statement from the American Heart Association. *Circulation*. 2011;123:1788-1830.

Pulmonary embolism (PE), submassive – Acute PE without systemic hypotension (systolic blood pressure \geq 90 mmHg) but with either right ventricular (RV) dysfunction or myocardial necrosis, where:

RV dysfunction is defined as the presence of at least 1 of the following:

- RV dilation (apical 4-chamber RV diameter divided by LV diameter $>$ 0.9) or RV systolic dysfunction on echocardiography;
- RV dilation (4-chamber RV diameter divided by LV diameter $>$ 0.9) on CT;
- Elevation of BNP ($>$ 90 pg/mL);
- Elevation of N-terminal pro-BNP ($>$ 500 pg/mL); or
- Electrocardiographic changes (new complete or incomplete right bundle-branch block, anteroseptal ST elevation or depression, or anteroseptal T-wave inversion).

Myocardial necrosis is defined as either of the following:

- Elevation of troponin I ($>$ 0.4 ng/mL) or
- Elevation of troponin T ($>$ 0.1 ng/mL).

Pulmonary embolism (PE), low-risk – Acute PE and the absence of the clinical markers of adverse prognosis that define massive or submassive PE.

Serious adverse events – Definition may be found in applicable regulations.

Serious adverse device effects – Definition may be found in applicable regulations.

Significant trapped thrombus in filter – Thrombus filling $>$ 25% of the filter.

Technical placement success – Deployment of filter in a location suitable to provide sufficient mechanical protection against PE with no filter deformation, fracture, premature release, or clinical migration.

Technical retrieval success – Endovascular retrieval of complete filter.

Unanticipated serious adverse device effects – Definition may be found in applicable regulations.

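### Enrollment is at sheath insertion but the Celect test set is defined by the filter received, so Celect attempts that end without a Celect in place can fall out of the effectiveness test

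*Combined protocol and SAP*

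**What the plan says.** - **Point of enrollment (7.2).** "Patients will be considered enrolled in the study once the filter introducer sheath is inserted below the skin". No filter has been deployed at that moment.
- **Stratum (1.0).** "patients will be stratified based upon the type of filter they receive".
- **Tested set (8.1).** "The study hypotheses will be tested only for patients receiving Celect" filters. Sections 8.1.1 and 8.1.2 repeat this restriction for effectiveness and safety.
- **Exit (7.13).** One of the events that end participation is "Device not implanted". Data up to exit are covered by a sentence that begins "Any data collected on the patient up to a participation endpoint (or until all queries involving the patient are resolved) may be used in the". This permits use and does not require it.
- **Endpoint (6.3.1, 8.1.1, Appendix C).** The primary effectiveness endpoint counts technical placement failure as well as new symptomatic PE. Technical placement success is "Deployment of filter in a location suitable to provide sufficient mechanical protection against PE with no filter deformation, fracture, premature release, or clinical migration".
- **Missing data (8.4).** Case deletion is the primary method while enough analyzable patients remain for power.

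No section defines an analysis set, gives a stratum to an enrolled patient who has no filter, or classifies a Celect attempt that ends with a Tulip.

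**The concern.** Membership of the tested set depends on part of the outcome being tested. To be tested as a Celect patient one must have received a Celect, and deployment is the first element of technical placement success. Two kinds of failure are affected:

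1. The sheath is inserted and no filter is deployed. The patient received neither filter, so belongs to neither stratum, and participation ends under 7.13.
2. A Celect attempt is abandoned and a Tulip is placed. By the filter received, the patient belongs to the Tulip stratum and could count there as a placement success.

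Both are failures of a Celect attempt. Removing them takes out failures and never successes, so any error moves the Celect rate up, towards the 90% goal. In a single-arm study judged against a fixed goal, no comparator would absorb such an error. The safety test has the same gap: an access site complication or procedure-related death in an enrolled patient with no implant has no stratum in which to count.

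**Working it through.** **Inputs from the documents.** Goal 90%, one-sided exact binomial test at 0.025 (8.1.1). Assumed Celect rate 98.4%, stated effectiveness N of 70, power 0.9, enrollment of 320, attrition of 72% (8.3). Earlier placement-failure figure 0.14% (Table 4.3). That row is labelled as placement success but stands in a table of adverse event rates, so I read it as a failure rate. It matches one event in 41 + 554 + 129 = 724 patients (1/724 = 0.14%).

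**Assumed input.** f, the share of Celect attempts that end without a Celect in place. The documents do not give it. I use 0.14%, 0.5%, 1%, 2% and 3%.

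**Step 1: the plan's own figures.** Take the smallest r with P(X ≥ r | n, p0) ≤ 0.025.
- Effectiveness, n = 70: r = 68, actual level 0.0242, power at 98.4% = 0.898, which rounds to 0.90.
- Safety, n = 88, goal 80%: r = 78, actual level 0.0238, power at 92.2% = 0.919.

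Both stated sizes reproduce, so the sample size calculation is not at fault.

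**Step 2: the pass rule when every attempt counts.**
- 320 evaluable: at least 299 successes (at most 21 failures), actual level 0.0206.
- After 72% attrition, 320 × 0.28 = 89.6, about 90 evaluable: at least 87 successes (at most 3 failures), actual level 0.0169.

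**Step 3: drop the attempts that end without a Celect.** Let the true rate over all attempts be exactly 90%. The dropped patients are all failures, so the rate among recipients is 0.90/(1 − f). The critical value is recomputed on the number of recipients, and the false-pass chance is averaged over the binomial number of recipients. Values with the number of recipients fixed at its rounded expectation are in brackets.

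| f | Rate among recipients | False pass, 320 evaluable | False pass, about 90 evaluable |
|---|---|---|---|
| 0.14% | 90.1% | 0.025 (0.024) | 0.019 (0.018) |
| 0.5% | 90.5% | 0.039 (0.040) | 0.024 (0.023) |
| 1% | 90.9% | 0.066 (0.072) | 0.034 (0.034) |
| 2% | 91.8% | 0.158 (0.144) | 0.064 (0.065) |
| 3% | 92.8% | 0.350 (0.350) | 0.113 (0.119) |

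With 320 evaluable the nominal 0.025 is passed once f rises much above 0.14%. With about 90 it is passed between 0.5% and 1%. The right-hand column treats the 90 as a simple binomial sample with the same f.

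**Step 4: effect at the planning assumption.** If 98.4% holds among recipients, the all-attempt rate is 0.984 × (1 − f): 98.3% at 0.14%, 97.4% at 1% and 96.4% at 2%. All are well above 90%.

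**The case against.** The strongest reply is that the literal reading is not the only one. Sections 1.0, 6.1 and 8.3 speak of enrolling 320 patients in the Celect stratum, and 7.2 puts enrollment at sheath insertion, so the stratum might be taken as settled before deployment. Section 3.1 describes sets with a preloaded filter and its sheath system, so the intended filter is normally known by then. Section 8.1.1 defines its parameter for a randomly selected patient, not an implanted one, and 7.13 allows data from patients without an implant to be used. This shows that the better analysis is possible. It does not specify it: none of these passages assigns the patient to a stratum or scores the failure, while 1.0 and 8.1 both name receipt. Even if such a patient were placed in the Celect stratum, the lack of a 12-month result could lead to case deletion under 8.4.

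The reply is right on several stronger readings that a reader might infer:

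- **That failed Celect placements in general leave the test.** They do not. Unsuitable location, deformation, fracture, premature release and clinical migration can all occur with a Celect deployed. Those patients received a Celect, stay in the test and count against it.
- **That section 4.0 shows the problem occurring.** It reports "one filter misplacement and migration requiring immediate retrieval and placement of a new filter", but that was a patient in a Tulip-only study whose first filter was deployed, and the event was reported. It is neither a non-deployment nor a switch from Celect to Tulip.
- **That the 5-23% for insertion problems in Table 4.1 estimates f.** It is a class-wide figure, and section 4.0 itself warns that definitions vary among publications.
- **That procedural harm is hidden.** Section 7.13 does not say that exit is immediate. Events seen before exit are reported under 12.2 and adjudicated under 12.1. At most, delayed events in a few patients may be missed.

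**Conclusion.** The mismatch between point of enrollment and tested set is real, and no text resolves it. Followed as written, the plan can overstate the Celect effectiveness rate, and only upwards. The documents do not support saying that it is overstated: that depends on f and on how the sponsor would in fact handle these patients.

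At the sponsor's earlier 0.14% the effect is negligible. That figure covers all placement failures in earlier studies of both filters, so it is only a rough guide to f. At 1% to 3% the false-pass chance is about 0.07 to 0.35 with 320 evaluable, which is the high case, and about 0.03 to 0.12 with about 90. These figures rest on an assumed f and on a true rate exactly at the 90% goal. The plan expects 98.4%, and at that rate the conclusion would be unlikely to change for small f. The correction is worth making because it is cheap and removes a bias of known direction.

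**What to change.** 1. In 1.0, 6.3 and 8.1, define the Celect stratum and tested set as all enrolled patients in whom Celect was the first filter attempted.
2. Score any such patient without a successfully placed Celect, whether left with no filter or switched to a Tulip, as an effectiveness failure, and exempt these patients from case deletion under 8.4.
3. Include access site complications and procedure-related deaths recorded in these patients in the Celect safety endpoint.
4. Report the as-received analysis as a sensitivity analysis.

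A 1-month contact for patients without an implant is optional. The fix does not depend on it.

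**Cost.** The change is wording, plus recording which filter was attempted first. Section 3.3 already has lot numbers of the devices used recorded. The effectiveness rate may become slightly less favourable. If 98.4% holds among recipients, power with 320 evaluable stays above 0.99 for f up to 2%. With about 90 evaluable it is 0.93, 0.80 and 0.60 at f = 0.14%, 1% and 2%. One dependency should be settled at the same time. If retrieved patients were removed from the denominator while every non-implant was kept, failures would be over-weighted: at f = 1%, 320 × 0.01 = 3.2 failures would stand against an allowance of 3 in 90. The plan should therefore state together how retrieved and non-implanted patients enter the denominator.

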2.0 Objective of the Clinical Study

The objectives of this study are to further evaluate the safety and effectiveness of Cook’s commercially available IVC filters (specifically, the Günther Tulip[®] filter and the Cook Celect[®] filters) in patients in need of temporary or permanent IVC filter placement for the prevention of PE. This study is intended to address FDA’s concerns related to IVC filters.⁴

3.0 Device Description and Intended Use

3.1 General Device Description

All Cook vena cava filter sets include an IVC filter intended for prevention of recurrent PE in specific situations, such as chronic, recurrent PE where anticoagulant therapy has failed or is contraindicated. All Cook vena cava filter sets are available in a femoral vein access version, with which the filter is introduced through the femoral vein, a jugular vein access version, with which the filter is introduced through the jugular vein, and a universal vein access version, which includes the components for both femoral and jugular vein approaches. Each filter set consists of a preloaded filter, a coaxial introducer sheath system with a Check-Flo[®] valve, a hydrophilically coated pre-dilator, and a three-way stopcock.

The jugular and femoral vein access versions of all filters are available with the NavAlign introducer system (K090140), with design improvements to the introducer sheath and filter introducer intended to ease the filter placement procedure and reduce the likelihood of procedure-related complications.

The femoral vein access version of all filters is available with a flexible tip (composed of flexible stainless steel cable tubing covered with polyether block amide (PEBAX) shrink tubing) on the filter introducer, which is intended to make the tip more flexible to improve trackability of the introducer through the venous anatomy (K121057).

The femoral vein access version of the Günther Tulip[®] filter and the Celect[®] filter is also available with added markers along the introducer sheath to improve visibility on procedural imaging (K112119). In this set, the femoral introducer sheath is made of polyethylene (as compared to fluorinated ethylene propylene, which is the material component of the femoral introducer sheath for all other femoral vein access sets) and has an attached clip (composed of stainless steel spring wire with polycarbonate, acrylonitrile/butadiene/styrene (PC-ABS) handle) to mark the position of the sheath at the insertion site.

The Celect[®] filter is available with added platinum markers on its primary legs to improve visibility on procedural imaging (K121629). The femoral vein access version of the Celect[®] with platinum markers on its primary legs is only available with a flexible tip, and is not available with markers along its introducer sheath.

Please reference the manufacturer's Instructions for Use (IFU) for a complete description of each of these devices.

3.2 Indication for Use

The Günther Tulip[®] filter and the Cook Celect[®] filters are intended for the prevention of recurrent PE via placement in the vena cava in the following situations:

- Pulmonary thromboembolism when anticoagulant therapy is contraindicated;
- Failure of anticoagulant therapy in thromboembolic diseases;
- Emergency treatment following massive PE where anticipated benefits of conventional therapy are reduced; and
- Chronic, recurrent PE where anticoagulant therapy has failed or is contraindicated.

In addition to the specific labeled indications, it is well-documented in clinical practice guidelines that IVC filters have additional clinical indications, and are frequently placed in patients with the following: severe trauma, closed head trauma, spinal cord injury,

multiple long-bone or pelvic fractures, or other conditions putting them at high risk for PE (e.g., prolonged immobilization, pre-/post-operatively).⁵⁻⁸ Outcomes from use in these broad patient populations have been widely reported in the literature^{1-3,9-22}, including those based on results of previous studies for the Cook IVC filters.¹⁻³ Based on available data, patient outcome is not specifically related to indication for filter placement, but may be related to each patient's overall medical condition, including the patient's state of hypercoagulability, body mass index, use of anticoagulation, comorbid conditions, etc. Moreover, Cook has conducted three previous studies of the performance of its permanent and retrievable IVC filters in a broad patient population,¹⁻³ and the results (or interim results) of these studies are included in product labeling. Furthermore, these broad patient populations were included in the indications for use that were approved in the PMA for the Cook Bird's Nest[®] Vena Cava Filter (P850049).

3.3 Device Identification and Tracking

As commercially available devices, the Cook IVC filters will be obtained by each site through normal commercial procurement methods and stored and accounted for following site-specific policies. Lot numbers for devices used in study patients will be recorded on the appropriate Case Report Forms (CRFs).

3.4 Instructions for Use

The manufacturer's IFU for each filter contains the following information:

- Complete instructions including storage and handling requirements, preparation for use, pre-use checks, precautions to be taken after use, and disposal.
- Complete summary of the necessary training and experience required for use of these devices.
- Complete description of the procedures involved in the use of these devices.

